5.6. Efficacy Endpoints in the Nonrandomized Full Analysis Set

The proportion of participants in clinical remission; symptomatic remission; endoscopic healing; Corticosteroid-free clinical remission; maintenance of clinical response; histologic-endoscopic mucosal healing; IBDQ remission; fatigue response; maintenance of clinical remission among the participants who had achieved clinical remission at maintenance baseline; and endoscopic normalization, all at Week M-44, and symptomatic remission at each visit through Week M-44, will be summarized descriptively based on the **Nonrandomized Full Analysis Set** (Section 4). The ICEs specified in Section 5.3.2. will be applied with ICE 2 (have a dose adjustment [including a sham dose adjustment]) excluded, and missing data rule (i.e., missing value will be imputed as non-responder) used for primary estimand will also be applied.

5.7. Efficacy in Participants Who Had a Dose Adjustment

The attributes and strategies for the ICEs that were used for the primary estimand for the primary endpoint analysis (Section 5.3.2.) will not be used for endpoints described in this section. The missing data rule used for primary estimand will be applied to symptomatic remission (i.e., missing value will be imputed as non-responder); however, for continuous data there will be no imputation for the missing data.

For the participants in the **Randomized Full Analysis Set** who had a dose adjustment (**Dose Adjustment Analysis Set**), the following endpoints at the time of dose adjustment and through 12 weeks after dose adjustment will be summarized and presented using descriptive statistics only (i.e., no statistical tests will be performed).

• Symptomatic remission

- Symptomatic response. Symptomatic response was defined as a decrease from induction baseline in the symptomatic Mayo Score by ≥30% and ≥1 point, with either a ≥1 point decrease from induction baseline in the rectal bleeding subscore or a rectal bleeding subscore of 0 or 1.
- Partial Mayo response
- CRP

In addition, the following summaries will be provided:

- The change in the Partial Mayo score from the time of dose adjustment through 12 weeks after dose adjustment.
- The change in CRP at or after 12 weeks from the time of dose adjustment.

5.8. Dose Adjustment as a Treatment Strategy

The attributes and strategies for the ICEs that were used for the primary estimand for the primary endpoint analysis (Section 5.3.2.) will also be used except that application of ICE 2 (i.e., have a dose adjustment) will be suspended for endpoints described in this section. The same analysis methods for the main estimands described in Section 5.3.2.1.1. and Section 5.4.1.3. will be used for the corresponding endpoints listed below.

The following endpoints will be presented by treatment group based on the **Randomized Full Analysis Set**:

- Clinical remission at Week M-44
- Symptomatic remission at Week M-44
- Symptomatic remission at each visit through Week M-44
- Endoscopic healing at Week M-44
- Corticosteroid-free clinical remission at Week M-44
- Clinical response at Week M-44
- Histologic-endoscopic mucosal healing at Week M-44
- IBDQ remission at Week M-44
- Fatigue response at Week M-44
- Clinical remission at Week M-44 among the participants who had achieved clinical remission at maintenance baseline.
- Endoscopic normalization at Week M-44
- Histologic healing at Week M-44
- Histologic remission at Week M-44

5.9. Safety Analyses

Safety data, including but not limited to, AEs and changes in laboratory assessments, will be summarized. Treatment-emergent AEs will be summarized by treatment group and Medical Dictionary for Regulatory Activities (MedDRA) system organ class and preferred terms.

Unless otherwise mentioned, safety summaries will be provided for the **Randomized Safety Analysis Set**, the **Nonrandomized Safety Analysis Set**, and the **Safety Analysis Set**. In general, participants will be analyzed according to their assigned treatment. However, participants assigned to placebo who incorrectly received guselkumab at any time during the maintenance phase (i.e., up to Week M-44) will be analyzed in the guselkumab group; participants assigned to guselkumab who received **only** placebo during the maintenance phase (i.e., up to Week M-44) will be analyzed in the placebo group.

For all continuous safety variables, descriptive statistics by treatment group will include the N, mean, standard deviation, median, minimum, and maximum. Categorical variables will be summarized by treatment group using frequency counts and percentages.

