9.4.3. Safety Analyses

Safety analyses will be based on the Safety Analysis Set (for the induction studies) or Randomized Safety Analysis Set (for the Maintenance Study), which is composed of all randomized participants with a modified Mayo score of 5 to 9 at induction baseline who receive at least 1 dose of study intervention. Safety summaries will also be provided for participants who are not randomized in the maintenance study who receive at least 1 dose of study intervention in maintenance, and for

all participants who receive at least 1 dose of study intervention in the maintenance study (including both randomized and nonrandomized participants).

Adverse Events

The verbatim terms used in the eCRF by investigators to identify AEs will be coded using the Medical Dictionary for Regulatory Activities. Any AE occurring at or after the initial administration of study intervention in each study is considered to be treatment-emergent for that study. All reported treatment-emergent AEs will be included in the analysis. For each AE, the percentage of participants who experience at least 1 occurrence of the given event will be summarized by intervention group.

The following analyses of AEs will be used to assess the safety of participants:

- Frequency and type of AEs.
- Frequency and type of SAEs.
- Frequency and type of reasonably related AEs as assessed by the investigator.
- Frequency and type of AEs leading to discontinuation of study intervention.
- Frequency and type of infections.
- Frequency and type of AEs temporally associated with infusion.
- Frequency and type of injection-site reactions.

Summaries, listings, datasets, or participant narratives may be provided, as appropriate, for those participants who die, who discontinue intervention due to an AE, or who experience a severe or a serious AE.

Clinical Laboratory Tests

The following summaries of clinical laboratory tests will be used to assess participant safety:

- Laboratory parameters and change from baseline in laboratory parameters (hematology and chemistry).
- Summary of maximum National Cancer Institute Common Terminology Criteria for Adverse Events (NCI-CTCAE) toxicity grade for postbaseline laboratory values (hematology and chemistry).
- Summary of elevated liver tests (to be defined in the SAP) will be provided.

Listings of participants with any abnormal postbaseline laboratory values of NCI-CTCAE grade ≥ 2 will also be provided.

Suicidal Ideation and Behavior

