1.3.1. Dose Adjustment

Participants in the randomized population with confirmed loss of clinical response (i.e., no longer satisfies the definition of clinical response as previously defined in Section 1.2) between Week M-8 and Week M-32 will be eligible to receive a single blinded dose adjustment as described below and shown in Figure 3:

[figure not shown]
- Guselkumab 200 mg SC q4w group: Participants will continue on guselkumab 200 mg SC q4w (i.e., sham dose adjustment).
- Guselkumab 100 mg SC q8w group: Participants will adjust to receive guselkumab 200 mg SC q4w.
- Placebo SC: Participants will adjust to receive guselkumab 200 mg SC q4w.

Guselkumab 24-week responders will continue to receive guselkumab 200 mg SC q4w and placebo responders at Week I-12 will continue to receive SC placebo. These participants are not eligible for a dose adjustment (they will undergo a sham dose adjustment to maintain the blind).

2771_v2

Participants who lost response will be assessed 12 weeks after the visit at which the loss of clinical response criteria are met and dose adjustment occurred. Participants who have not achieved a partial Mayo response (i.e., a decrease from induction baseline of ≥ 2 in the partial Mayo score) at 12 weeks after loss of clinical response will be discontinued from study intervention administration at that time.

Figure 3: Dose Adjustment Treatment Groups in the Maintenance Study for Participants in Clinical Response Following Induction

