5.2. Participant Disposition

The number of participants in the following disposition categories through M-44 will be summarized by treatment group and overall based on the Full Analysis Set (including both randomized and nonrandomized participants), the All Treated Analysis Set, and the Dose Adjustment Analysis Set:

- Participants who received study intervention
- Participants who discontinued study intervention
 - Reasons for discontinuation of study intervention (including COVID-19 and the regional crisis)
- Participants who terminated study prematurely
 - Reasons for termination of study (including COVID-19 and the regional crisis)

Listings of participants based on the **All Treated Analysis Set** will be provided for the following categories:

- Participants who discontinued study intervention
- Participants who terminated study prematurely

In addition, the number and percentage of participants who have a dose adjustment over time will be summarized for participants in the **Randomized Full Analysis Set**.

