5.9.1. Extent of Exposure

The number and percentage of participants who receive study intervention through M-44 will be summarized based on the **Enrolled Analysis Set**. The number of administrations of study intervention received, the cumulative dose of study intervention, and the average duration of follow-up in weeks will be summarized by treatment group through M-44 based on **Randomized Safety Analysis Set**, the **Nonrandomized Safety Analysis Set**, and the **Safety Analysis Set**.

The distribution of participants by study intervention lot through Week M-44 will also be provided based on the **All Treated Analysis Set**.

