5.9.2. Adverse Events

The verbatim terms used in the CRF by investigators to identify adverse events will be coded using the Medical Dictionary for Regulatory Activities (MedDRA). Any AE occurring at or after the initial administration of study intervention of this maintenance study is considered to be treatment emergent. All reported treatment-emergent adverse events will be included in the analysis. For each adverse event, the number and percentage of participants who experience at least 1 occurrence of the given event will be summarized by treatment group. Since safety should be assessed relative to exposure and follow-up, all AE summary tables will summarize the average weeks of follow-up and average exposure (number of administrations) for each treatment group.

Type of AEs to assess the safety of participants:

Summary tables will be provided for the following treatment-emergent adverse events (TEAEs):

- AEs (including infections)
- SAEs (SAEs including serious infections)
- Reasonably related AEs as assessed by the investigator

- AEs of severe intensity
- AEs leading to discontinuation of study intervention
- Injection-site reactions

Overall TEAE summary table and number of TEAEs per hundred subject-years of follow-up through Week M-44 for the events above (except for injection-site reactions) will also be provided.

An overall TEAE summary table of events through Week M-44 and frequency and type of AEs will also be provided for the All Treated Analysis Set, Safety All Randomized and Treated Analysis Set, and Safety All Nonrandomized and Treated Analysis Set.

In addition to the summary tables, listings will be provided for participants in the **All Treated Analysis Set** who:

- Had SAEs
- Had AEs of severe intensity
- Had AEs leading to discontinuation of study intervention
- Died
- AE of special interest (malignancy and tuberculosis)
- Other AEs of interest (e.g., opportunistic infections, MACE [CV death, nonfatal MI, nonfatal stroke], drug-related hepatic disorders, venous thromboembolism (VTE), anaphylactic reactions, and serum-sickness)

The above AEs will either be presented in a listing or described in the clinical study report. A list of AEs of special interest and other AEs of interest are provided in Appendix 7.

Definitions

- A reasonably related AE is defined as any event with a relationship to study agent of 'Very likely', 'Probable', or 'Possible' on the AE eCRF page or if the relationship to study agent is missing.

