5.9.3. Additional Safety Assessments

5.9.3.1. Clinical Laboratory Tests

Laboratory assessments include, but are not limited to, the assessments listed below:

• Hematology: hemoglobin, hematocrit, platelet count, total and differential WBC count.

• Blood chemistry: total and direct bilirubin, alanine aminotransferase (ALT), aspartate aminotransferase (AST), alkaline phosphatase, albumin, total protein, calcium, phosphate, sodium, potassium, chloride, blood urea nitrogen (BUN), and creatinine.

The maintenance baseline value for a participant is the value closest to but prior to the first dose of study agent of the maintenance study unless specified otherwise. In addition, change from maintenance baseline is defined to be the assessment at the post-maintenance baseline visit minus the assessment at maintenance baseline. There will be no imputation for missing laboratory values.

Laboratory parameters and change from maintenance baseline in laboratory parameters (hematology and chemistry) through Week M-44 will be summarized and displayed by treatment group based on the **Randomized Safety Analysis Set** and **the Nonrandomized Safety Analysis Set**.

The following summaries will also be presented through Week M-44 for the **Randomized Safety Analysis Set**, the **Nonrandomized Safety Analysis Set**, and the **Safety Analysis Set**:

- Summary of maximum modified National Cancer Institute Common Terminology Criteria for Adverse Events (NCI-CTCAE) toxicity grade for post-maintenance baseline laboratory values through Week M-44 for the predefined hematology and chemistry lab parameters except for liver tests (i.e., ALT, AST, alkaline phosphatase, and total bilirubin). This summary will also be presented for the **All Treated Analysis Set**. Shift tables for maximum modified NCI-CTCAE toxicity grade from maintenance baseline through Week M-44 will be summarized for the predefined hematology and chemistry lab parameters except for liver tests (i.e., ALT, AST, alkaline phosphatase, and total bilirubin).
- Summary of maximum post-maintenance baseline measurement through Week M-44 for liver tests (i.e., ALT, AST, alkaline phosphatase, and total bilirubin) relative to ULN threshold. This summary will also be presented for the All Treated Analysis Set, the Safety All Randomized, the Treated Analysis Set, and the Safety All Nonrandomized and Treated Analysis Set.

Line graphs will also be provided for ALT, AST, total bilirubin, and alkaline phosphatase.

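### Maintenance safety tables by assigned arm mix placebo and 100 mg q8w follow-up with time on guselkumab 200 mg q4w after the planned dose adjustment

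*SAP*

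**What the plan says.** SAP 1.3.1 and Protocol 6.6.1 build in a single blinded regimen change for re-randomized participants who lose clinical response between M-8 and M-32. For the control arm: "Placebo SC: Participants will adjust to receive guselkumab 200 mg SC q4w". The 100 mg q8w arm moves to the same regimen. The 200 mg q4w arm has only a sham adjustment.

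SAP 5.9 sets the grouping rule for safety: "In general, participants will be analyzed according to their assigned treatment". For the placebo arm its one exception is "participants assigned to placebo who incorrectly received guselkumab at any time during the maintenance phase", who are moved to the guselkumab group.

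The outputs that follow are all by group to M-44:
- SAP 5.9.1: the number of administrations, "the cumulative dose of study intervention, and the average duration of follow-up in weeks will be summarized by treatment group through M-44".
- SAP 5.9.2: all treatment-emergent events from the first maintenance dose, as number and percentage with an event, and for most categories as "number of TEAEs per hundred subject-years of follow-up through Week M-44".
- SAP 5.9.3.1: laboratory summaries, for example "Summary of maximum post-maintenance baseline measurement through Week M-44 for liver tests".

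Protocol 9.4.3 is no different: "the percentage of participants who experience at least 1 occurrence of the given event will be summarized by intervention group".

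**The concern.** Safety of the maintenance regimens is a primary objective (SAP 1.1). A reader will take the placebo column as the reference and the 100 mg q8w column as the low-dose experience. As planned, both also hold events and person-time on the highest maintenance regimen, and no table shows how many. A real excess on 200 mg q4w could be diluted in the between-column contrast. A low-dose signal could also be attributed to the wrong regimen.

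The SAP deals with the same switch explicitly in other places, so its absence from 5.9 looks like an omission rather than a considered choice.

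**Working it through.** **1. Does the exception cover the planned switch?** No. It applies to guselkumab received in error. A protocol-directed dose adjustment is not an error, so switchers stay in the placebo column. The exception does not address 100 mg q8w participants moving to 200 mg q4w at all.

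**2. Is there a time cut?** None is stated in SAP 5.9.1, 5.9.2 or 5.9.3, or in Protocol 9.4.3. Events count from the first maintenance dose and all are included. The exposure figure shown with the AE tables is the number of administrations, which does not separate placebo from guselkumab injections.

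**3. How is the switch handled elsewhere?**
- Efficacy: an intercurrent event in SAP 5.3.2, with dedicated analyses in 5.7 and 5.8.
- PK: data after a dose increase are excluded from the by-visit analyses (5.10.1.1).
- Immunogenicity: participants who did and did not increase dose are summarized separately (5.10.2.1). In 5.10.2.3 the cut applies only to the two serum-concentration displays.
- The Dose Adjustment Analysis Set is used for disposition (5.2), efficacy (5.7), baseline characteristics (Appendix 3) and medications (Appendix 5), but for no safety table.

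**4. How large could the mixing be?** The plan has no figure to reproduce. All inputs below are assumptions except the 44-week period, the M-8 to M-32 window and the 12-week rule (Protocol 4.1.3.1 and 6.6.1).

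Let f = proportion switching, t = mean switch week, and s = share of switchers stopped at 12 weeks for lack of partial Mayo response. Those stopped have their last dose at about t+8 and a safety visit about 12 weeks later, so post-switch follow-up is d = min(44 − t, 20).

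Share of arm follow-up after the switch = f[(1−s)(44−t) + s·d] / {(1−f)·44 + f[(1−s)·44 + s(t+d)]}

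Apparent rate ratio = R / (1 − share + R·k·share), with R = 2 the assumed true ratio and k = the background rate after the switch relative to the rest of the arm.

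| Arm | f | t | s | Share | Apparent ratio (k = 1) |
|---|---|---|---|---|---|
| Placebo | 0.2 | 24 | any | 4/44 = 0.091 | 2/1.091 = 1.83 |
| Placebo | 0.4 | 12 | 0 | 12.8/44 = 0.291 | 2/1.291 = 1.55 |
| Placebo | 0.4 | 12 | 0.5 | 10.4/41.6 = 0.250 | 2/1.250 = 1.60 |
| Placebo | 0.4 | 12 | 1 | 8/39.2 = 0.204 | 2/1.204 = 1.66 |
| 100 mg q8w | 0.1 | 24 | any | 2/44 = 0.045 | 2/1.045 = 1.91 |
| 100 mg q8w | 0.2 | 12 | 0 | 6.4/44 = 0.145 | 2/1.145 = 1.75 |
| 100 mg q8w | 0.2 | 12 | 1 | 4/41.6 = 0.096 | 2/1.096 = 1.82 |

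Wider bounds with no one stopping: 10% switching at M-32 gives 0.10 × 12/44 = 2.7%; 50% at M-8 gives 0.50 × 36/44 = 40.9%.

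**5. Is the direction certain?** No, because switchers are selected for loss of response. With the 200 mg arm's rate held fixed:

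| Share | k = 0.25 | k = 0.5 | k = 1 | k = 2 |
|---|---|---|---|---|
| 0.091 | 2.10 | 2.00 | 1.83 | 1.57 |
| 0.291 | 2.34 | 2.00 | 1.55 | 1.07 |

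These figures bear on the per-100-subject-year table only, not on the percentage-with-event tables.

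**The case against.** The case against acting has several parts.

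- **By-assigned-arm safety tables are valid.** They describe the assigned strategy, adjustment included. This stands, and they should be kept.
- **Some planned output is unmixed.** The randomized 200 mg q4w column contains one regimen. So do the nonrandomized groups: induction placebo responders stay on placebo, and guselkumab 24-week responders stay on 200 mg q4w. This is true and useful, but these groups are selected differently and do not separate the two mixed randomized columns.
- **Partial mitigations exist.** SAP 5.2 plans that "the number and percentage of participants who have a dose adjustment over time will be summarized". Cumulative dose is shown by group. Listings or report narratives cover serious, severe and selected events, and listings cover abnormal laboratory values. For rare serious events these may tell as much as a rate would. None of them, though, gives rates by regimen received.
- **The added columns would be small.** With 161 per arm and no one stopping, placebo switchers would number about 32 to 64, contributing 161 × 0.2 × 20/52 ≈ 12 to 161 × 0.4 × 32/52 ≈ 40 person-years. The 100 mg arm would contribute about 6 to 20. Rates of serious events would be imprecise. This stands, and it is a reason to keep the tables descriptive.
- **The ratios are assumed.** Nothing in the documents supports R = 2, least of all for 200 mg q4w against 100 mg q8w, and SAP 5.9 plans no rate ratio. This also stands: the figures show scale only.
- **Table shells, which are not among the documents, might add a split.** They might, and the SAP does not forbid it, but it does not plan one.

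**Conclusion.** The concern holds. Followed as written, SAP 5.9 leaves post-adjustment events and person-time on guselkumab 200 mg q4w in the placebo and 100 mg q8w columns, and no planned table separates them.

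Confidence is high for what the SAP specifies; it does not extend to what undisclosed table shells may contain. The size cannot be computed from the documents. Under the assumed switch rates and timings, roughly 9-29% of placebo-arm and 5-15% of 100 mg-arm follow-up would be post-switch. Any contrast would move toward no difference if background risk is equal, and in an unknown direction if it is not.

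This is a point to consider rather than a flaw in the trial's main conclusions. The primary endpoint, Type I error and induction safety are untouched, and nothing here questions the dose-adjustment rule itself.

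**What to change.** Keep the by-assigned-arm tables. In SAP 5.9.1 to 5.9.3, for the Randomized Safety Analysis Set, add descriptive tables of exposure, AEs, SAEs, infections and laboratory values that count events and follow-up only up to dose adjustment (sham adjustment in the 200 mg q4w arm). Show post-adjustment events and person-time in separate columns: placebo to 200 mg q4w, and 100 mg q8w to 200 mg q4w.

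State two limits beside them:
1. The cut depends on outcome and falls differently by arm, so these tables do not give an unbiased on-regimen comparison.
2. Early placebo follow-up carries residual induction guselkumab. The only duration in the text is 12 weeks after the last dose, in the contraception criterion of Protocol 5.1. With the last induction dose four weeks before M-0, that is about M-8, and it is a rough guide only.

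The cost is low: SAP wording and extra descriptive tables from dates already collected, with no new data and no change to any planned table.
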